3.1.1. Dose Escalation Rules

[figure not shown]
Each dose cohort will consist of 8 subjects (6:2; PMN310:placebo). To evaluate the short term safety and tolerability of PMN310, each cohort will enroll a sentinel group of 2 subjects (1:1, PMN310:placebo) who will be dosed prior to dosing the remaining 6 subjects in the cohort (5:1, PMN310:placebo). The first two sentinel subjects for Cohort 1 (age < 50) will have MRIs performed and read locally. The SRC will review all safety data collected through 48 hours postdose from the 2 sentinel subjects to determine the acceptability of proceeding with dosing of the remaining 6 subjects in the cohort. Additional details on the SRC are provided in Section 3.1.2.

Dose escalation to the next cohort will only occur after approval by the SRC. The SRC will determine the acceptability of proceeding with enrollment of the next cohort based on review of safety and any available PK data at the time of review through 7 days postdose for a minimum of 6 of 8 subjects per cohort. Doses to be evaluated are presented in Section 5.2.1.

In the event that important safety concerns are observed at any time during the study, administration of study drug will be paused, subjects in the subsequent cohort(s) will not receive further study drug until further review of the safety data has occurred, and subsequent recommendations and approval have been provided by the SRC. Dose escalation/stopping rules are detailed in Section 5.5.

A schematic illustrating the study design is provided in Figure 1.

Figure 1: PMN310-101 Study Schema Per Cohort

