5.5. Dose Escalation/Stopping Rules

Dose escalation will be paused for review if any of the following occur, Two or more of the subjects in a cohort develop Grade ≥ 2 AEs in the same category.

- One or more subjects in a cohort develop Grade ≥ 3 AEs.
- It is determined that the limit of safety and/or tolerability has been reached as determined by the SRC.

The Sponsor or SRC may pause and then stop dosing within a cohort or decide to not dose escalate to a higher dose if it is determined that any AE is occurring that is intolerable or poses a medically unacceptable safety risk.

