7.1.15.2. Assessment of Adverse Event Severity

The Investigator will assess the intensity of each AE and SAE reported during the study on the basis of his or her clinical judgement.

The classifications in Table 1 should be used in assigning intensity of each AE recorded in the CRF.

Table 1: Classification of Adverse Events by Intensity

Intensity (Grade)	Definition						
Mild AE (Grade 1)	An event that is easily tolerated by the subject, causing minimal discomfort and not interfering with everyday activities.						
Moderate AE (Grade 2)	Some interference with activity not requiring medical intervention						
Severe AE (Grade 3)	 Prevents daily activity and requires medical intervention An event that, at the time of occurrence, put the subject at risk of death or resulted 						
	in a persistent or significant disability or incapacity.An event that resulted in death						

AE = adverse event

Any AE that changes in intensity or grade during a single occurrence of an AE will be recorded in the CRF at the highest level experienced by the subject.

An AE that is assessed as severe should not be confused with an SAE. Severity is a category used for rating the intensity of an AE (such as mild, moderate, or severe myocardial infarction). An AE, however, may be of relatively minor medical significance (e.g., a severe headache). Both AEs and SAEs can be assessed as severe. An AE is considered serious when it meets criteria for one of the predefined outcomes described in Section 7.1.15.1.

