8.3. Replacement of Study Subjects

Sentinel group subjects who discontinue before Day 7 will be replaced, unless they discontinued due to an SAE related to study drug.

Non-sentinel group subjects who discontinue before Day 7 may be replaced at the discretion of the Sponsor and the SRC.

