# 5.3 Dose Escalation/Stopping Rules

Each dose cohort will consist of 8 subjects (6:2; PMN310:placebo). To evaluate the short term safety and tolerability of PMN310, each cohort will enroll a sentinel group of 2 subjects (1:1, PMN310:placebo) who will be dosed prior to dosing the remaining 6 subjects in the cohort (5:1, PMN310:placebo). The Safety Review Committee (SRC) will review all safety data collected through 48 hours postdose from the 2 sentinel subjects to determine the acceptability of proceeding with dosing of the remaining 6 subjects in the cohort.

Dose escalation to the next cohort will only occur after approval by the SRC. The SRC will determine the acceptability of proceeding with enrollment of the next cohort based on review of safety and any available PK data at the time of review through 7 days postdose for a minimum of 6 of 8 subjects per cohort.

Dose escalation will be paused for review if any of the following occur,

- Two or more of the subjects in a cohort develop Grade ≥ 2 AEs in the same category.
- One or more subjects in a cohort develop Grade  $\geq 3$  AEs.
- It is determined that the limit of safety and/or tolerability has been reached as determined by the SRC.

The Sponsor or SRC may pause and then stop dosing within a cohort or decide to not dose escalate to a higher dose if it is determined that any AE is occurring that is intolerable or poses a medically unacceptable safety risk.

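### The pause triggers in protocol 5.5 and SAP 5.3 use grade, count and AE category but not seriousness, so a single drug-related SAE below Grade 3 does not automatically pause escalation

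*Protocol*

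**What the plan says.** Protocol 5.5 lists three reasons to pause escalation for review, and SAP 5.3 repeats them:

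1. "Two or more of the subjects in a cohort develop Grade ≥ 2 AEs in the same category"
2. "One or more subjects in a cohort develop Grade ≥ 3 AEs"
3. The SRC determines that the limit of safety or tolerability has been reached.

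A closing sentence adds that the Sponsor or SRC may pause or stop dosing, or decline to escalate, for any AE they find intolerable or medically unacceptable.

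Protocol 3.1.1 has a broader clause: "In the event that important safety concerns are observed at any time during the study, administration of study drug will be paused". It does not say what counts as such a concern, and it sends the reader back to the list: "Dose escalation/stopping rules are detailed in Section 5.5". The same section requires SRC approval for every escalation, based on data through 7 days postdose from at least 6 of 8 subjects.

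On severity, protocol 7.1.15.2 says: "An AE that is assessed as severe should not be confused with an SAE". It gives a severe headache as an example of an event that may be medically minor. Protocol 7.1.15.1 sets out six SAE criteria. Its hospitalization criterion includes being kept for observation, and doubtful cases are to be counted as serious.

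A drug-related SAE does appear as a rule elsewhere. Under protocol 8.3 and SAP 5.4, sentinel subjects who leave before Day 7 are replaced "unless they discontinued due to an SAE related to study drug".

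**The concern.** The event triggers rank events by severity, and the protocol itself says that severity is not seriousness. Read literally, the list pauses escalation for one severe, non-serious headache whatever its cause, because the Grade 3 trigger has no relatedness condition. It does not pause for one SAE that the Investigator attributes to study drug but grades as moderate.

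The subjects are healthy volunteers with no expected direct benefit (protocol 1.5). The minimum data for an escalation decision are 7 days on 6 of 8 subjects, while AEs are collected to Week 12. A related SAE can therefore arise after its own cohort has been reviewed. What is at stake is whether escalation is held by rule or by discretion while that event is reviewed.

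**Working it through.** The plan states no operating characteristic for the pause rule, and protocol 9.2 says the sample size is not statistically based. There is no figure to reproduce, so the check compares the texts.

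**Step 1. Do the triggers mention seriousness?** Triggers 1 and 2 use grade, number of subjects and (trigger 1) AE category. Trigger 3 is an SRC judgement. Triggers naming an SAE: 0 of 3, in both documents.

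**Step 2. Which SAEs can fall below Grade 3?** The criteria in protocol 7.1.15.1 are death, life-threatening, hospitalization, incapacity, congenital anomaly and other important medical event: 6. By its wording, Table 1 in 7.1.15.2 places three of these at the severe end (death, risk of death, persistent or significant disability or incapacity).

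- Not placed there by Table 1: 6 − 3 = 3.
- Less congenital anomaly, which is not a dosed subject's own event: 3 − 1 = 2.

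Hospitalization and other important medical event remain, so 2 of 6. This counts criteria, not events.

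**Step 3. How much of those two is left?** Grade 2 is defined as "Some interference with activity not requiring medical intervention", so by wording an admission for treatment is not Grade 2. Grade 3, however, requires both that daily activity is prevented and that medical intervention is needed. An event that needs intervention but does not prevent daily activity fits neither definition, and its grade is left to clinical judgement. The clear remainder is observation-only and doubtful admissions, with some important medical events.

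**Step 4. Apply the event triggers to single scenarios within a cohort.**

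| Event | Trigger 1 | Trigger 2 | Automatic pause |
|---|---|---|---|
| 1 fatal, life-threatening or disabling SAE | not needed | met | yes |
| 1 severe, non-serious headache | no (1 < 2) | met | yes |
| 2 subjects with non-serious Grade 2 AEs, same category | met | no | yes |
| 1 related Grade 2 SAE and a second subject with a Grade 2 AE in that category | met | no | yes |
| 1 related SAE at Grade 1 or 2, no such second subject | no (1 < 2) | no (below 3) | **no** |

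**Step 5. What covers the last row?**

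- Trigger 3 and the closing sentence of 5.5: judgement, the latter worded as may.
- The 3.1.1 clause: mandatory in form, but it depends on an undefined term.
- SRC approval before each escalation: always required, but the outcome is judgement.
- 24-hour SAE reporting (7.1.15.8) and Medical Monitor review (7.1.15.1): these ensure awareness, not a pause.
- Study termination (8.1): possible after consultation.

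None of these makes the last row an automatic pause. The documents give no event rate and the conclusion needs none, so no probability is attached.

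**The case against.** The strongest objection is that this is a legitimate design choice with good cover. Escalation is closed by default: nothing proceeds until the SRC approves, and the list only adds pauses to that gate. The SRC includes the Investigator, who reports the SAE, and the Medical Monitor, who reviews it. The 3.1.1 clause applies at any time and has no grade floor. Most SAEs that need intervention would be graded 3. A single moderate event in a cohort of 8, possibly serious only because of the rule for doubtful admissions, is arguably what a committee should judge case by case. The severe headache that does trigger a pause must itself prevent daily activity and need intervention, so pausing for it is not odd. The use of related SAEs in the replacement rule creates no contradiction with 5.5.

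Much of this stands. It limits the finding to a narrow residual and rules out two stronger readings that a reader might infer. One is that a drug-related SAE could pass unnoticed, or that escalation would simply carry on. The reporting, Medical Monitor and SRC approval provisions do not support that. The other is that every related SAE should stop all dosing automatically through 3.1.1. Every subject has lumbar punctures on Day 3 and Day 29. A rating of possible requires only a reasonable time sequence, even where another cause may explain the event (7.1.15.3). A post-puncture event kept for observation could then halt administration in every cohort, which is too heavy a response to write in as a rule.

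The objection does not show that the case in the last row of the table is covered by rule. Seriousness and causality are also Investigator judgements, but both are defined, recorded and already required for each SAE, whereas the term in 3.1.1 is not defined.

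**Conclusion.** The point holds in a limited form and is a cheap improvement, not a serious defect. A single drug-related SAE below Grade 3, with no second subject having a Grade 2 or higher AE in the same category, does not automatically pause escalation under protocol 5.5 or SAP 5.3. Review before further escalation rests on the SRC's approval of each step and on the undefined term in 3.1.1. The case for a written trigger is clearest for an SAE that arises after the 7-day review of its cohort.

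This rests on reading Table 1 and the SAE definition as worded. It is also confined to the protocol and SAP text. The SRC charter, the three protocol clarification letters cited in SAP 3.1 and the published grading scale cited in protocol 1.5 were not available, and any of them may already name SAEs. The charter's scope as described in protocol 3.1.2 does not mention stopping criteria, and 5.5 refers to none of these sources.

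**What to change.** Add one item to the list in protocol 5.5 and SAP 5.3:

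> One or more subjects in any cohort develop an SAE considered possibly or probably related to study drug, regardless of grade, at any time through the Week 12 visit.

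Escalation then pauses for SRC review under the existing lead-in sentence. Leave it to the SRC whether dosing within an ongoing cohort also stops, and do not link the new item to the 3.1.1 clause. Add a matching line to the SRC charter if it has none.

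No new data are needed: relatedness is already defined as possible or probable in 7.1.15.3, and causality must be rated before an SAE report is sent. The cost is an occasional extra SRC review and a short delay. Some of these reviews will concern placebo subjects, since causality is rated blind, or lumbar-puncture events rated possible.

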5.6. Storage, Handling, and Accountability of Study Drug

PMN310 will be supplied directly to the study site. The study site will acknowledge receipt of the shipment and record inventory and usage of study drug on a drug disposition form. Upon arrival at the study site, vials will be stored frozen at -25°C to -15°C (-13°F to 5°F) inside the cartons to minimize exposure to light, with the cartons oriented such that the enclosed vials are in the upright position. An unblinded study monitor will perform reconciliation of the drug product.

Used vials will be destroyed according to the site's policy for investigational drug destruction. Unused vials will be either destroyed at the study site or returned to the Sponsor, as agreed between the site and Sponsor. Before disposal/destruction of unused vials, final drug accountability and reconciliation must be performed by the unblinded study monitor. Documentation of destruction of vials of PMN310 must be available for review by the study monitor.

5.7. Prior and Concomitant Therapy

5.7.1. Prohibited Medications

All medications, including over-the-counter, herbal, or homeopathic preparations (except for acetaminophen as needed for miscellaneous aches and pains), are prohibited during the study, unless required to be administered for the treatment of an AE. Subjects receiving a stable dose of medications for high blood pressure or high cholesterol may be included with Sponsor approval.

6. STUDY PROCEDURES BY PERIOD

The scheduled assessments for Screening, Inpatient, and Outpatient periods are summarized in Appendix 1.

For each study day described below, when multiple procedures are scheduled at the same nominal time relative to dosing, the following chronology of events should be adhered to, where possible:

- Vital signs and ECGs will be obtained as close as possible to the scheduled time (up to 45 minutes before PK sampling), but before blood specimen collection.
- Serum PK samples will be obtained at the scheduled time.
- After venipuncture, PK samples will be obtained first followed by clinical safety laboratory tests.

In the case of a clinical or laboratory abnormality, the Investigator may apply clinical judgement in repeating the measurement if the abnormality is believed likely to be an error.

6.1. Screening Period (Day -28 to Day -1)

Healthy volunteers will be recruited for this clinical study. Before initiation of screening assessments, the subject must be given a complete explanation of the purpose and procedures occurring during the study. Subsequently, the subject must sign and receive a copy of an Institutional Review Board (IRB)-approved informed consent form (ICF) (Section 11.4). Once informed consent has been obtained, screening assessments will be performed and eligibility of the subject will be determined based on the inclusion and exclusion criteria. Subjects who fail screening may be rescreened following Sponsor approval.

Study assessments are described in Section 7.

The following evaluations will be performed to assess the subject's eligibility for the study:

- Demography and medical history
- Suicidality evaluation: C-SSRS (Baseline Screening version)
- Height
- Complete physical examination
- Neurologic examination
- Vital signs
- Weight
- MRI
- Lumbar x-rays (at investigator's discretion to rule out any contraindication to lumbar puncture)
- 12-lead ECG
- HBsAg and HCV tests

- FSH (post-menopausal women only)
- Pregnancy test (non-post-menopausal women only)
- Urine drug, urine cotinine, and serum alcohol screen
- Clinical laboratory tests:
 - Blood chemistry and hematology
 - Urinalysis
 - Coagulation
- Review of concomitant medications
- AE assessment of protocol related procedures only, to be performed after informed consent is obtained

The Investigator may use clinical judgment when determining the clinical significance of laboratory results throughout the study. The Medical Monitor may, depending on study criteria, be consulted before enrollment of a candidate with abnormal laboratory values.

6.2. Inpatient Period (Days -1, 1, 2, 3, and 4)

During the inpatient period, standardized breakfast, lunch, and dinner will be provided at fixed times. Meals are to be consumed within 45 minutes. Evening snacks will be provided at a consistent time each day. Fluids will be allowed liberally.

6.2.1.1. Day -1 (Day of Admission to the Study Clinic)

On Day –1 eligibility will be confirmed and eligible subjects will be admitted to the study clinic. Admission should occur before 6 PM.

The following assessments will be performed:

- Complete physical examination
- Neurologic examination
- Vital signs
- Weight
- 12-lead ECG
- Pregnancy test (non-post-menopausal women only)
- Urine drug, urine cotinine, and serum alcohol screen
- Clinical laboratory tests:
 - Blood chemistry and hematology
 - Urinalysis
 - Coagulation
- ADA serum sampling

- Residual and unused serum samples will be stored for future use for the measurement of biomarkers
- Review of concomitant medications
- AE assessment of protocol related procedures only

The subject will remain in the study clinic overnight.

6.2.1.2. Day 1 (Day of Study Drug Administration)

Subjects will be randomly assigned to study drug (PMN310 or placebo). After consumption of a standard breakfast, and pre-dosing assessments, study drug will be administered as an IV infusion as described in Section 5.2. After administration of study drug, inpatient follow-up data collection will include the following:

- C-SSRS (Since Last Visit version)
- Vital signs
- 12-lead ECG
- PK serum sampling: before infusion, at the end of infusion (see Section 5.2.1 for a definition for complete infusion), and at 0.5, 1, 2, 4, 8, and 12 hours after the end of infusion.
 - Acceptable windows for PK sampling are as follows (exact time of PK collection is to be recorded):
 - Pre-dose sample to be collected within 60 minutes prior to dosing
 - 0.5 to 4-hour post-dose samples to be collected \pm 5 minutes
 - 8 to 12-hour post-dose samples to be collected \pm 10 minutes
- Review of concomitant medications
- AE assessment

The subject will remain in the study clinic overnight.

6.2.1.3. Day 2

On Day 2, subjects will undergo the following assessments:

- Vital signs
- 12-lead ECG
- PK serum sampling at 24 and 36 hours from end of Day 1 infusion
 - Acceptable windows for PK sampling are ± 30 minutes (exact time of PK collection is to be recorded)
- Review of concomitant medications
- AE assessment

The subject will remain in the study clinic overnight.

6.2.1.4. Day 3

On Day 3 subjects will undergo the following assessments:

- Symptom directed physical examination
- Neurologic examination
- Vital signs
- Weight
- 12-lead ECG
- Clinical laboratory tests:
 - Blood chemistry and hematology
 - Urinalysis
 - Coagulation
- PK serum sampling 72 hours from end of Day 1 infusion
 - Acceptable window for PK sampling is ± 60 minutes (exact time of PK collection is to be recorded)
- LP. INR/PT/partial thromboplastin time (PTT) and platelet results within 2 days prior to the LP must be confirmed and determined to be within normal range before LP.
- Review of concomitant medications
- AE assessment

The subject will remain in the study clinic overnight.

6.2.1.5. Day 4

On Day 4, subjects will undergo the following assessments:

- C-SSRS (Since Last Visit version)
- Vital signs
- PK serum sampling 96 hours from end of Day 1 infusion
 - Acceptable window for PK sampling is ± 60 minutes (exact time of PK collection is to be recorded)
- Review of concomitant medications
- AE assessment

Following the completion of assessments, unless the Investigator feels that a longer period of observation is warranted (e.g., due to side effects of the study drug or any study procedure), subjects will be discharged from the study clinic.

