- ⁶ Vital signs should always be collected up to 45 minutes before PK sampling (i.e., nominal time) unless otherwise indicated before infusion, at the end of infusion (see Section 5.2.1 for a definition for complete infusion), and at 0.5, 1, 2, 4, 8, and 12 hours after the end of infusion. Day 2 (24 and 36 hours), D3 (48 hours), and Day 4 (72 hours), Days 8, 15, 29, 43, 85. Subjects should be resting supine for at least 5 minutes before the vital sign assessment; the exact time of assessment is to be recorded.
- Only subjects ≥ 50 years of age will have MRI assessments at Day 43. If ARIA is detected, repeat MRIs will be performed every 3-4 weeks until ARIA is resolved.
- ⁸ ECGs should always be performed up to 45 minutes before PK Sampling (i.e., nominal time) unless otherwise indicated before infusion, at the end of infusion, and at 1, 2, 4, 8, and 12 hours after the end of infusion. Day 2 (24 and 36 hours), D3 (48 hours), and Day 4 (72 hours), Days 8, 29, and 85.

Date of discharge from the inpatient study clinic is at the discretion of the Investigator. It may be extended, if needed, and is dependent on the need for further observation and/or care.

PMN310-101 Version 1.0, 10 March 2023

- ⁹ FSH will be evaluated for post-menopausal women only. Post-menopausal status will be confirmed through testing of FSH levels (≥ 40 IU/mL).
- ¹⁰ Pregnancy test is not required for post-menopausal women. Serum human chorionic gonadotropin at Screening and urinary chorionic gonadotropin thereafter. If a urine pregnancy test is positive, a serum pregnancy test must be obtained. Additional details provided in Section 7.1.9.
- ¹¹ Pharmacokinetic blood sampling for serum PMN310 concentrations should be performed as follows:
 - Day 1: before infusion, at the end of infusion, and at 0.5, 1, 2, 4, 8, and 12 hours after the end of infusion
 - o Acceptable windows for PK sampling are as follows (exact time of PK collection is to be recorded):
 - Pre-dose sample to be collected within 60 minutes prior to dosing
 - 0.5 to 4-hour post-dose samples to be collected \pm 5 minutes
 - 8 to 12-hour post-dose samples to be collected \pm 10 minutes
 - Day 2 (24 and 36 hours)
 - Acceptable window for PK sampling is ± 30 minutes (exact time of PK collection is to be recorded)
 - Day 3 (48 hours) and Day 4 (72 hours)
 - \circ Acceptable windows for PK sampling are \pm 60 minutes (exact time of PK collection is to be recorded)
 - Days 8, 15, 29, 43, 57, 85

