-  Symptom directed physical examination and neurological examination will be performed at the indicated timepoints.
-  Vital signs should always be collected up to 45 minutes before PK sampling (i.e., nominal time) unless otherwise indicated before infusion, at the end of infusion (see protocol Section 5.2.1 for a definition for complete infusion), and at 0.5, 1, 2, 4, 8, and 12 hours after the end of infusion. Day 2 (24 and 36 hours), D3 (48 hours), and Day 4 (72 hours), Days 8, 15, 29, 43, 85. Subjects should be resting supine for at least 5 minutes before the vital sign assessment; the exact time of assessment is to be recorded.
-  Only subjects ≥ 50 years of age will have MRI assessments at Day 43. If ARIA is detected, repeat MRIs will be performed every 3-4 weeks until ARIA is resolved.
-  ECGs should always be performed up to 45 minutes before PK Sampling (i.e., nominal time) unless otherwise indicated before infusion, at the end of infusion, and at 1, 2, 4, 8, and 12 hours after the end of infusion. Day 2 (24 and 36 hours), D3 (48 hours), and Day 4 (72 hours), , 8, 29, and 85.

CONFIDENTIAL Page 12 of 32

-  Pregnancy test is not required for post-menopausal women. Serum human chorionic gonadotropin at Screening and urinary chorionic gonadotropin thereafter. If a urine pregnancy test is positive, a serum pregnancy test must be obtained. Additional details provided in protocol Section 7.1.9.
-  Pharmacokinetic blood sampling for serum PMN310 concentrations should be performed as follows:
  - Day 1: before infusion, at the end of infusion, and at 0.5, 1, 2, 4, 8, and 12 hours after the end of infusion
    - o Acceptable windows for PK sampling are as follows (exact time of PK collection is to be recorded):
      - Pre-dose sample to be collected within 60 minutes prior to dosing
      - 0.5 to 4-hour post-dose samples to be collected  $\pm$  5 minutes
      - 8 to 12-hour post-dose samples to be collected  $\pm$  10 minutes
  - Day 2 (24 and 36 hours)
    - $\circ$  Acceptable window for PK sampling is  $\pm$  30 minutes (exact time of PK collection is to be recorded)
  - Day 3 (48 hours), Day 4 (72 hours) and Day 5 (96 hours)
    - $\circ$  Acceptable windows for PK sampling are  $\pm$  60 minutes (exact time of PK collection is to be recorded)
    - O Day 5 (96) hours does not require inpatient collection
  - Days 8, 15, 29, 43, 57, 85

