# 6.4.2 Data Handling

All assessments collected at scheduled and unscheduled days and time points will be included in the listings. For parameters that will be summarized by day and time point, the nominal day and time point as recorded in the CRF will be used. When the data from a scheduled assessment is not available, an unscheduled assessment within the assessment window defined in the Schedule of Assessments, if available, will be used to replace the scheduled assessment. If multiple unscheduled assessments are present in the assessment window, the unscheduled assessment closest to the nominal day and time point will be used. This algorithm will be implemented for chemistry, hematology, coagulation, and urinalysis labs, 12-lead ECG, vital signs, PK concentrations, ADA results, and exploratory biomarkers.

Note that blood draws for international normalized ratio/prothrombin time/partial thromboplastin time, and platelets may be drawn a day before a scheduled lumbar puncture to ensure results are available in time for the lumbar puncture procedure. The blood draw results that were obtained a day early will be analyzed with the scheduled blood draw results.

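### Protocol Sections 6.2.1.4 and 6.2.1.5 time the Day 3 and Day 4 serum PK samples 24 h later than those study days allow, and disagree with Appendix 1 and SAP Table 1

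*Protocol*

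**What the plan says.** Three schedules cover the same serum draws.

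- **Protocol Section 6.2.1 (visit lists).** Day 2: "PK serum sampling at 24 and 36 hours from end of Day 1 infusion". Day 3 (6.2.1.4): "PK serum sampling 72 hours from end of Day 1 infusion". Day 4 (6.2.1.5): "PK serum sampling 96 hours from end of Day 1 infusion". For Day 3 and again for Day 4: "Acceptable window for PK sampling is ± 60 minutes (exact time of PK collection is to be recorded". No 48 h sample is listed. Discharge follows the Day 4 assessments.
- **Protocol Appendix 1, footnote 11.** "Day 3 (48 hours) and Day 4 (72 hours", with the same ± 60 min and no 96 h sample. Footnote 6 times vital signs to match: "Day 2 (24 and 36 hours), D3 (48 hours), and Day 4 (72 hours), Days 8, 15, 29, 43, 85". Footnote 8 does the same for ECGs on Days 2 to 4.
- **SAP Table 1, footnote 11.** "Day 3 (48 hours), Day 4 (72 hours) and Day 5 (96 hours", with a Day 5 column that the protocol schedule lacks and a note that the Day 5 draw need not be inpatient.

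The opening of protocol Section 7 points to both Appendix 1 and Section 6. Section 7.1.10, which is specific to PK, points to Appendix 1 only.

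For analysis by day and time point, SAP Section 6.4.2 says "the nominal day and time point as recorded in the CRF will be used". SAP Section 9.1.1 summarises serum concentrations and plots means by nominal time. It estimates non-compartmental (NCA) parameters from actual times, with nominal time as a fallback if the actual time is unknown. SAP Section 9.2 compares CSF with serum at nominal times that have both values.

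**The concern.** The Day 3 and Day 4 entries in Section 6.2.1 each name a study day and an hour that cannot both be met. A site working from Section 6 has two ways to go wrong. It can draw on the stated day and label the sample 24 h late, so that a 48 h concentration enters the 72 h row and a 72 h concentration enters the 96 h row. Or it can keep to the stated hour and take nothing between 36 h and 72 h.

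Each cohort has only 6 subjects on PMN310, so a few affected draws matter to a row of the concentration table. Under SAP Section 9.1.1 a row loses its summary statistics once more than 25% of values are missing or below quantification. One missed 48 h draw of 6 is 16.7%; two are 33.3%, which suppresses the row.

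Day 3 is also a mandatory lumbar puncture day in every cohort, so its serum partner is one of the disputed samples.

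**Working it through.** **1. Calendar check.** Let *h* be the clock hour on Day 1 when the infusion and flush end, and *t* the hours after that. Then

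study day = floor((h + t) / 24) + 1.

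The Day 2 entry comes first, because it fixes the convention. With h = 10:

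- t = 24: 34/24 gives Day 2
- t = 36: 46/24 gives Day 2
- t = 48: 58/24 gives Day 3
- t = 72: 82/24 gives Day 4
- t = 96: 106/24 gives Day 5

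So the protocol's Day 2 hours reproduce (36 h does so for any infusion ending before noon), and its Day 3 and Day 4 hours do not. For every *h* tried from 08:00 to 18:00, and at t − 1, t and t + 1, 48 h stays on Day 3, 72 h on Day 4 and 96 h on Day 5.

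**2. Can the window rescue it?** The earliest permitted 72 h draw is at 71 h. It falls on Day 3 only if h + 71 < 72, that is, if the infusion ended before 01:00 on Day 1. The same bound applies to 95 h on Day 4. Protocol Section 6.2.1.2 doses after breakfast, so neither is possible. The discrepancy is 24 h against a window of 1 h either side.

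**3. Discharge.** Four nights from Day −1 are the nights of Days −1, 1, 2 and 3, with discharge on Day 4. A 96 h sample falls on Day 5, after the planned discharge.

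**4. Schedules side by side.**

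| Source | Day 3 | Day 4 | Day 5 |
|---|---|---|---|
| Calendar | 48 h | 72 h | 96 h |
| Protocol 6.2.1.4 and 6.2.1.5 | 72 h | 96 h | none |
| Protocol Appendix 1, fn 11 | 48 h | 72 h | none |
| SAP Table 1, fn 11 | 48 h | 72 h | 96 h |

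**5. Size of a 24 h label error.** The documents give no half-life or other PK value, so both calculations rest on assumptions.

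- *Mono-exponential decline*: the fall per 24 h is 1 − 2^(−1/t½), with t½ in days. This gives 2.4% at 28 days, 4.8% at 14 days and 9.4% at 7 days.
- *Two-compartment antibody model* (V1 = V2 = 3 L; CL 0.15, 0.25, 0.4 L/day; Q 0.3, 0.5, 0.9 L/day; terminal half-life about 12 to 32 days): C72/C48 = 0.80 to 0.88 and C96/C72 = 0.83 to 0.91, a fall of about 10-20% per 24 h. A value drawn at 48 h and labelled 72 h would read 1/0.88 − 1 to 1/0.80 − 1 too high, about 13-25% before rounding of the ratios.

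The second range is larger because distribution is still under way at 48 to 96 h in that model.

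**The case against.** The case for treating this as minor has real force.

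- **Appendix 1 governs PK timing.** A reader might infer that sites have no guide to which schedule applies. Section 7.1.10 refers PK collection to Appendix 1 alone, and the vital-sign and ECG footnotes anchor Days 3 and 4 to 48 h and 72 h. This stands and makes the error less likely in practice. It does not remove the incorrect hours from the visit lists.
- **It may already be corrected.** SAP Section 3.1 cites three clarification letters dated after protocol v2.0, and the coherent Day 3/4/5 schedule in SAP Table 1 may come from one of them. The letters are not among the documents, so it cannot be said that the error was still live when the SAP was written, nor that it was resolved.
- **The PK parameters are protected.** A reader might infer that Cmax, AUC, half-life or the power model would be biased. NCA uses actual times, both protocol schedules require the exact time to be recorded, and dose proportionality is built on the NCA parameters. A wrong label alone does not reach them. What remains is the nominal fallback when the actual time is unknown, and the fact that NCA cannot recover a sample that was never drawn.
- **CSF pairing.** A reader might infer that the Day 3 CSF:serum comparison is wrong whenever the serum label is wrong. Serum and CSF drawn together on Day 3 remain a true pair whatever hour is printed. The comparison suffers only if the serum draw is delayed or the two labels do not match.
- **Mislabelling is not shown.** It depends on CRF labels that are not in the documents.

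**Conclusion.** The contradiction holds and needs no pharmacological assumption: two sampling instructions in Protocol Section 6.2.1 are each exactly 24 h later than their study day permits. The 48 h sample is missing there, and the status of a 96 h sample differs across the three schedules.

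The consequence is limited. The direct exposure is in the nominal-time serum summaries and mean plots, and conditionally in the CSF:serum comparison. A skipped 48 h draw would be a genuine loss of data, but the documents do not show that this or any mislabelling would in fact occur.

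The effect of a 24 h mislabel cannot be derived from the plan. The ranges of about 2-9% (mono-exponential, half-life 28 to 7 days) and about 10-20% (two-compartment) are illustrations; treating the larger one as the expected error would go beyond the documents. This is worth correcting because it is an operative sampling rule that cannot be followed as written and is cheap to repair.

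**What to change.** 1. Reconcile Protocol Sections 6.2.1.4 and 6.2.1.5, Appendix 1 footnote 11 and SAP Table 1 so that each study day carries one nominal hour consistent with the calendar. Decide in the same step whether the Day 5 (96 h) draw belongs in the protocol schedule, and make all three agree.
2. Before drafting, check whether one of the clarification letters cited in SAP Section 3.1 already does this. If so, cite it in the SAP beside Table 1.
3. Add a sentence to SAP Section 6.4.2 or 9.1.1: for any subject sampled under the conflicting text, the nominal time for these draws is the scheduled hour nearest the recorded actual time, and draws outside ± 60 min are flagged and kept. Leaving late draws unassigned would be a mistake, since two of 6 without a row would trigger the 25% suppression rule.

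The cost is a wording change or clarification letter if none exists, one SAP sentence and a small programming derivation. It needs no samples beyond those SAP Table 1 already lists.
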